5.2.5 Accountability and dispensation

Drug accountability and dispensation will occur through the Department of Pharmacy Investigational Drugs and all standard operating procedures of the University of Texas MD Anderson Cancer Center.

5.2.6 Disposition of unused investigational study drug

The site will account for all investigational study drug dispensed and also for appropriate destruction. Certificates of delivery and destruction must be maintained as part of Institutional current standard operating procedures.

6. TREATMENT PLAN

6.1 Subject enrollment

Patients who have signed informed consent and have undergone screening will be enrolled onto this study and can begin therapy. There is no randomization. This is a single arm, open-label presurgical pilot study prior to the initiation of standard neoadjuvant chemotherapy of the physician's choice for patients with clinical stage II-III HR+/HER2- breast cancer. Patients who are unable to complete all

scheduled study requirements including the pre and post treatment breast biopsies can be replaced at the request of [name] and/or [name] and/or the study team.

6.1.1 Procedures for handling subjects incorrectly enrolled

Subjects who are incorrectly enrolled, but not yet initiated on treatment will be withdrawn from the study and replaced.

6.2 Dosage and Administration

Patients will receive 1500 mg durvalumab via IV infusion q4w +/- 3 days for 2 doses/cycles and 75 mg tremelimumab via IV infusion q4w +/- 3 days for 2 doses/cycles. Dosing outside the window should be discussed with [name] and/or [name]. Tremelimumab will be administered first. Durvalumab infusion will start approximately 1 hour after the end of tremelimumab infusion. The duration will be approximately 1 hour for each infusion. A 1-hour observation period is required after the first infusion of durvalumab and tremelimumab. If no clinically significant infusion reactions are observed during or after the first cycle, subsequent infusion observation periods can be at the Investigator's discretion (suggested 30 minutes after each durvalumab and tremelimumab infusion).

6.3 Dose Modification and Toxicity Management

6.3.1 Durvalumab and tremelimumab

For adverse events (AEs) that are considered at least partly due to administration of durvalumab the following dose adjustment guidance may be applied:

- Treat each of the toxicities with maximum supportive care (including holding the agent suspected of causing the toxicity where required).
- If the symptoms promptly resolve with supportive care, consideration should be given to continuing the same dose of durvalumab or tremelimumab along with appropriate continuing supportive care. If medically appropriate, dose modifications are permitted for durvalumab and tremelimumab (see Appendix 1).
- All dose modifications should be documented with clear reasoning and documentation of the approach taken.

In addition, there are certain circumstances in which durvalumab or tremelimumab should be permanently discontinued.

Following the first dose of durvalumab or tremelimumab, subsequent administration of durvalumab or tremelimumab can be modified based on toxicities observed (see Appendix 1).

Based on the mechanism of action of durvalumab or tremelimumab leading to T-cell activation and proliferation, there is the possibility of observing immune related Adverse Events (irAEs) during the conduct of this study. Potential irAEs include immune-mediated enterocolitis, dermatitis, hepatitis, and endocrinopathies. Subjects should be monitored for signs and symptoms of irAEs. In the absence of an

alternate etiology (e.g., infection or PD) signs or symptoms of enterocolitis, dermatitis, hepatitis, and endocrinopathy should be considered to be immune-related.

Dose modification recommendations and toxicity management guidelines for immune-mediated reactions, for infusion-related reactions, and for non-immune-mediated reactions are detailed in Appendix 1.

In addition, management guidelines for adverse events of special interest (AESIs) are detailed in appendix 1. All toxicities will be graded according to NCI CTCAE v4.03.

7. RESTRICTIONS DURING THE STUDY AND CONCOMITANT TREATMENT(S)

7.1 Restrictions during the study

The following restrictions apply while the patient is receiving study treatment and for the specific times before and after:

– Females of childbearing potential who are sexually active with a non-sterilized male partner must use at least 1 **highly** effective method of contraception (Table 3) from the time of screening and must agree to continue using such precautions for 180 days after the last dose of durvalumab + tremelimumab combination therapy. Non-sterilized male partners of a female patient must use male condom plus spermicide throughout this period. Cessation of birth control after this point should be discussed with a responsible physician. Not engaging in sexual activity for the total duration of the drug treatment and the drug washout period is an acceptable practice; however, periodic abstinence, the rhythm method, and the withdrawal method are not acceptable methods of birth control. Female patients should also refrain from breastfeeding throughout this period.

N.B Females of childbearing potential are defined as those who are not surgically sterile (ie, bilateral tubal ligation, bilateral oophorectomy, or complete hysterectomy) or post-menopausal.

Women will be considered post-menopausal if they have been amenorrheic for 12 months without an alternative medical cause. The following age-specific requirements apply:

- Women <50 years of age would be considered post-menopausal if they have been amenorrheic for 12 months or more following cessation of exogenous hormonal treatments and if they have luteinizing hormone and follicle-stimulating hormone levels in the post-menopausal range for the institution or underwent surgical sterilization (bilateral oophorectomy or hysterectomy).
- Women \geq 50 years of age would be considered post-menopausal if they have been amenorrheic for 12 months or more following cessation of all exogenous hormonal treatments, had radiation-induced menopause with last menses >1 year ago, had

chemotherapy-induced menopause with last menses >1 year ago, or underwent surgical sterilization (bilateral oophorectomy, bilateral salpingectomy or hysterectomy).

Highly effective methods of contraception, defined as one that results in a low failure rate (ie, less than 1% per year) when used consistently and correctly are described in Table 3. Note that some contraception methods are not considered highly effective (e.g. male or female condom with or without spermicide; female cap, diaphragm, or sponge with or without spermicide; non-copper containing intrauterine device; progestogen-only oral hormonal contraceptive pills where inhibition of ovulation is not the primary mode of action [excluding Cerazette/desogestrel which is considered highly effective]; and triphasic combined oral contraceptive pills).

Table 3 Highly Effective methods of contraception (<1% failure rate)

Barrier/Intrauterine methods	Hormonal Methods

 • Copper T intrauterine device • Levonorgestrel-releasing intrauterine system (eg, Mirena®)^a 	
 • Etonogestrel implants: e.g. Implanon or Norplan • Intravaginal device: e.g. ethinylestradiol and etonogestrel • Medroxyprogesterone injection: e.g. Depo-Provera • Normal and low dose combined oral contraceptive pill • Norelgestromin/ethinylestradiol transdermal system • Cerazette (desogestrel)

^a This is also considered a hormonal method

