4.1 Inclusion criteria

For inclusion in the study, patients should fulfill the following criteria:

1. Written informed consent and any locally-required authorization (e.g., HIPAA) obtained from the subject prior to performing any protocol-related procedures, including screening evaluations
2. Age \geq 18 years at time of study entry
3. Eastern Cooperative Oncology Group (ECOG) performance status of 0 or 1
4. Hormone receptor positive (defined as estrogen receptor [ER] and/or progesterone receptor [PR] positive), HER2 negative breast cancer that is clinically staged II-III with no known metastatic disease. ER and/or PR defined as positive if expression $>10\%$ by immunohistochemistry (IHC). HER2 negative or non-amplified as determined by the current ASCO-CAP criteria which are as follows: HER2 testing by IHC as 0 or 1+. If HER2 is 2+, ISH (in situ hybridization) must be performed. HER2 is positive if:
 - IHC 3+ based on circumferential membrane staining that is
 - complete, intense
 - ISH positive based on:
 - Single-probe average HER2 copy number ≥ 6.0 signals/cell.
 - Dual-probe HER2/CEP17 ratio ≥ 2.0 ;c,e with an average HER2 copy number ≥ 4.0 signals/cell
 - Dual-probe HER2/CEP17 ratio ≥ 2.0 ;c,e with an average HER2 copy number < 4.0 signals/cell
 - Dual-probe HER2/CEP17 ratio < 2.0 ;c,e with an average HER2 copy number ≥ 6.0 signals/cell
5. Chemotherapy is planned for the patient in the neoadjuvant setting
6. Adequate normal organ and marrow function as defined below:
 - Haemoglobin ≥ 9.0 g/dL
 - Absolute neutrophil count (ANC) $\geq 1.5 \times 10^9/L$ (≥ 1500 per mm^3)
 - Platelet count $\geq 100 \times 10^9/L$ ($\geq 100,000$ per mm^3)

- Serum bilirubin $\leq 1.5 \times$ institutional upper limit of normal (ULN). This will not apply to subjects with confirmed Gilbert's syndrome (persistent or recurrent hyperbilirubinemia that is predominantly unconjugated in the absence of hemolysis or hepatic pathology), who will be allowed only upon treating physician, Principle Principal Investigators (PI) or co-PI approval.
- AST (SGOT)/ALT (SGPT) $\leq 2.5 \times$ institutional upper limit of normal unless liver metastases are present, in which case it must be $\leq 5 \times$ ULN
- Creatinine CL > 40 mL/min by the Cockcroft-Gault formula (Cockcroft and Gault 1976) or by 24-hour urine collection for determination of creatinine clearance:

Males:

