4.2 Exclusion criteria

Subjects should not enter the study if any of the following exclusion criteria are fulfilled:

1. Involvement in the planning and/or conduct of the study (applies to both AstraZeneca staff and/or staff at the study site)
2. Participation in another clinical study with an investigational product during the last 1 month prior to initiation of therapy
3. Any previous treatment with a PD1 or PD-L1 inhibitor, including durvalumab or an anti-CTLA4, including tremelimumab
4. History of another primary malignancy except for:

- Malignancy treated with curative intent and with no known active disease ≥ 5 years before the first dose of study drug and of low potential risk for recurrence
 - Adequately treated non-melanoma skin cancer or lentigo maligna without evidence of disease
 - Adequately treated carcinoma in situ without evidence of disease eg, cervical cancer in situ
5. Has received therapy for this current diagnosis of breast cancer including endocrine therapy or chemotherapy
 6. A single QT interval corrected for heart rate (QTc) ≥ 470 . If an ECG is interpreted to be a prolonged QT interval, 2 additional ECGs will be obtained and the PI will then evaluate all 3 ECGs to determine whether the patient should be excluded. Mean QT interval corrected for heart rate (QTc) ≥ 470 ms calculated from 3 electrocardiograms (ECGs) using Fredericia's Correction
 7. Current or prior use of immunosuppressive medication within 28 days before the first dose of durvalumab or tremelimumab, with the exceptions of intranasal and inhaled corticosteroids or systemic corticosteroids at physiological doses, which are not to exceed 10 mg/day of prednisone, or an equivalent corticosteroid
 8. Active or prior documented autoimmune disease within the past 2 years NOTE: Subjects with vitiligo, Grave's disease, or psoriasis not requiring systemic treatment (within the past 2 years) are not excluded.
 9. Active or prior documented inflammatory bowel disease (e.g., Crohn's disease, ulcerative colitis)
 10. History of primary immunodeficiency
 11. History of allogeneic organ transplant
 12. History of hypersensitivity to durvalumab or tremelimumab or any excipient
 13. History of hypersensitivity to the combination or comparator agent (if applicable)

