7.2.2 Excluded Concomitant Medications

The following medications are considered exclusionary during the study.

1. Any investigational anticancer therapy other than the protocol specified therapies.
2. Any concurrent chemotherapy, radiotherapy (except palliative radiotherapy), immunotherapy, biologic or hormonal therapy for cancer treatment.
3. Immunosuppressive medications including, but not limited to systemic corticosteroids at doses not exceeding 10 mg/day of prednisone or equivalent, methotrexate, azathioprine, and TNF- α blockers. Use of immunosuppressive medications for the management of investigational product-related AEs or in subjects with contrast allergies is acceptable. In addition, use of inhaled and intranasal corticosteroids is permitted. A temporary period of steroids will be allowed for different indications, at the discretion of the principal investigator (e.g., chronic obstructive pulmonary disease, radiation, nausea, etc).
4. Live attenuated vaccines within 30 days of durvalumab and tremelimumab dosing (ie, 30 days prior to the first dose, during treatment with durvalumab and tremelimumab for 30 days post discontinuation of durvalumab and tremelimumab. Inactivated vaccines, such as the injectable influenza vaccine, are permitted.

Table 4. Prohibited and Rescue Medications

Prohibited medication/class of drug:	Usage:
Additional investigational anticancer therapy concurrent with those under investigation in this study	Should not be given whilst the patient is on IP treatment
mAbs against CTLA-4, PD-1, or PD-L1	Should not be given whilst the patient is on IP treatment through 90 days after the last dose of IP.
Any concurrent chemotherapy, local therapy (except palliative radiotherapy for non-target lesions, eg, radiotherapy, surgery, radiofrequency ablation), biologic therapy, or hormonal therapy for cancer treatment	Should not be given whilst the patient is on IP treatment (including SoC). (Concurrent use of hormones for non-cancer-related conditions [eg, insulin for diabetes and hormone replacement therapy] is acceptable.)

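### Table 3 lists three oestrogen-containing contraceptives, and Table 4 accepts unspecified hormone replacement, without caution, in a trial limited to ER- and/or PR-positive tumours with no prior therapy

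*Combined protocol and SAP*

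**What the plan says.** **Population.** Section 4.1, item 4, admits only disease that is "Hormone receptor positive (defined as estrogen receptor [ER] and/or progesterone receptor [PR] positive". Section 4.2, item 5, excludes anyone who "Has received therapy for this current diagnosis of breast cancer including endocrine therapy or chemotherapy".

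**Contraception.** Section 7.1 applies to women of childbearing potential who are sexually active with a non-sterilized male partner. They must use at least one highly "effective method of contraception (Table 3) from the time of screening" and continue for 180 days after the last dose. Table 3 gives the qualifying methods, which include:
- "Normal and low dose combined oral contraceptive pill"
- "Intravaginal device: e.g. ethinylestradiol and etonogestrel"
- "Norelgestromin/ethinylestradiol transdermal system"

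The copper T device is also listed, and Section 7.1 accepts abstinence for the whole period.

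**Other hormones.** Section 7.2.2 and its Table 4 prohibit hormonal therapy given as cancer treatment. Table 4 then adds: "Concurrent use of hormones for non-cancer-related conditions [eg, insulin for diabetes and hormone replacement therapy] is acceptable". Appendix 1 (endocrinopathy, Grade 2) names sex hormones among the replacement therapies that may be started for an immune-related endocrine event.

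**The concern.** The trial is defined by hormone-receptor expression, and the primary tumour is in place and untreated when the contraception requirement begins. The same protocol lists oestrogen-containing products as ways of meeting that requirement. This goes further than leaving a detail out, because the site is given a list on which a combined pill counts as compliant. A woman could stay on one, or start one at screening, and be fully within protocol. Table 4 leaves a similar opening for a patient taking menopausal oestrogen.

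What is at stake is consistent guidance to the site and a sensible default for patients. It is not the validity of an analysis.

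**Working it through.** The plan states no figure to reproduce. The check is a count, a time window and a reading of the provisions on hormones.

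**1. Count of Table 3 entries.** There are 2 in the barrier/intrauterine column and 6 in the hormonal column, so 2 + 6 = 8.

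| Type | Entries | Number |
|---|---|---|
| Non-hormonal | copper T device | 1 |
| Progestogen-only | levonorgestrel intrauterine system, etonogestrel implant, medroxyprogesterone injection, desogestrel pill | 4 |
| Oestrogen-containing | ethinylestradiol vaginal device, combined pill, ethinylestradiol patch | 3 |

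Check: 1 + 4 + 3 = 8. Deleting the three oestrogen-containing entries leaves 8 − 3 = 5, of which 1 is non-hormonal and 4 are progestogen-only.

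**2. How long the requirement lasts.**
- Screening: up to 28 days before Day 1 (Section 8.1.1).
- First to second dose: four weeks plus the 3-day window, 28 + 3 = 31 days (Section 5.2.1).
- After the last dose: 180 days (Section 7.1).
- Total: 28 + 31 + 180 = 239 days at most on schedule. Dose holds or dosing outside the window could lengthen it.

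This is the length of the contraception requirement. It is not a measured exposure, and the tumour is not untreated throughout, because chemotherapy is due within 28 days of the last infusion (Section 5.2.2).

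**3. Does any provision restrict oestrogen?**
- Section 7.1 rules out some methods, but only on contraceptive failure rate. Receptor status is not mentioned.
- Section 4.2, item 5, and the hormonal exclusions in Section 7.2.2 concern treatment of the cancer. They do not reach contraceptives or menopausal replacement.
- Section 7.2 requires the Principal Investigator to be told of all medication. That is a duty to report and gives no instruction on oestrogen.
- Table 4 does not say which replacement hormones it means. Appendix 1 counts sex hormones as hormone replacement, so the term as this protocol uses it does not exclude oestrogen.

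No caution was found in the eligibility criteria, Section 7 or Appendix 1.

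**4. How many patients.** The documents do not give the number of women using or likely to use oestrogen. With 15 patients planned, it lies between 0 and 15.

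**The case against.** The strongest reply is that Table 3 is not prescribing advice. It is defined by a failure rate below 1% per year, so it says which methods prevent pregnancy reliably and leaves suitability to the physician, who will know the tumour's receptor status. The documents contain nothing on the hazard of oestrogen over this time frame, and the consent pages, which were not available, may carry the advice. All of that stands, and it keeps the point small. It does not remove it. The tables are what the site follows, and consent advice against oestrogen would still leave them to be aligned.

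A second reply is that Table 4 means thyroid or steroid replacement, since the phrase sits beside insulin and Section 10.1.3 speaks of hormone replacement for immune-related events. That may well be the intention. The wording does not say so, and Appendix 1 uses the term more widely.

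A third is that the remedy is uneven: if the oncologist's agreement suffices for progestogens in tumours that may be PR positive, it could suffice for oestrogen too. This is a fair point of clinical judgement. The case for deletion is that it costs little with five methods left, whereas deleting every hormonal method would leave only the copper T device on the list.

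Two stronger readings fail. A reader might infer that the protocol pushes women onto hormones. It does not: the copper T device and abstinence are accepted, and the requirement does not apply where the partner is sterilized. A reader might also see a contradiction where Section 7.1 calls a "non-copper containing intrauterine device" not highly effective while Table 3 lists the levonorgestrel system. The specific listing in Table 3, with its own footnote, settles that.

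**Conclusion.** The point holds as a minor, inexpensive improvement to the safety text. In a receptor-positive population with no prior therapy, 3 of 8 listed contraceptives contain oestrogen, and Table 4 does not exclude oestrogen replacement. The requirement that Table 3 serves runs for up to about 239 days on schedule.

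The conclusion rests on one assumption from outside the documents: that exogenous oestrogen deserves caution in such patients. No size of risk is claimed.

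A reader might go on to infer that hormone use would bias the immune results, and that Section 11.6 should flag users. The documents do not support this. They give no evidence of such an effect, and the immune analysis is descriptive. The schedule also marks medication review only at screening and Day 1 of each cycle, not at the visit before chemotherapy, so a flag running to the second biopsy would lack a scheduled source. Feasibility, the ETOX rule and the sample size are unaffected.

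**What to change.** 1. **Table 3.** Delete the ethinylestradiol vaginal device, the combined pill and the ethinylestradiol patch. Add below the table: *A non-hormonal method (copper T) is preferred. Progestogen-only methods are used only if the treating oncologist agrees, because the tumour may be PR positive. A woman using an oestrogen-containing method at screening changes to a listed method without a gap in contraception.*
2. **Table 4.** Replace the examples in the sentence on hormones for non-cancer conditions with: *insulin for diabetes, thyroid hormone or physiological corticosteroid replacement; systemic oestrogen is not allowed.* Add that any sex-hormone replacement under Appendix 1 for an immune-related endocrinopathy must be agreed with both the endocrinologist and the treating oncologist, so that necessary endocrine care stays possible.

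The cost is a few lines at the next amendment, with no new visit, test or analysis, and the consent form should be checked for agreement. The downside is a slightly shorter list of contraceptive options.

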7.2 Concomitant treatment(s)

The Principal Investigator must be informed as soon as possible about any medication taken from the time of screening until the end of the clinical phase of the study (final study visit). Any concomitant medication(s), including herbal preparations, taken during the study will be recorded in the electronic medical record.

Restricted, prohibited, and permitted concomitant medications are described in the following tables.

7.2.1 Permitted concomitant medications

Investigators may prescribe concomitant medications or treatments (e.g., acetaminophen, diphenhydramine) deemed necessary to provide adequate prophylactic or supportive care except for those medications identified as “excluded” as listed in Section 7.2.2.

7.2.2 Excluded Concomitant Medications

The following medications are considered exclusionary during the study.

1. Any investigational anticancer therapy other than the protocol specified therapies.
2. Any concurrent chemotherapy, radiotherapy (except palliative radiotherapy), immunotherapy, biologic or hormonal therapy for cancer treatment.
3. Immunosuppressive medications including, but not limited to systemic corticosteroids at doses not exceeding 10 mg/day of prednisone or equivalent, methotrexate, azathioprine, and TNF- α blockers. Use of immunosuppressive medications for the management of investigational product-related AEs or in subjects with contrast allergies is acceptable. In addition, use of inhaled and intranasal corticosteroids is permitted. A temporary period of steroids will be allowed for different indications, at the discretion of the principal investigator (e.g., chronic obstructive pulmonary disease, radiation, nausea, etc).
4. Live attenuated vaccines within 30 days of durvalumab and tremelimumab dosing (ie, 30 days prior to the first dose, during treatment with durvalumab and tremelimumab for 30 days post discontinuation of durvalumab and tremelimumab. Inactivated vaccines, such as the injectable influenza vaccine, are permitted.

Table 4. Prohibited and Rescue Medications

Prohibited medication/class of drug:	Usage:
Additional investigational anticancer therapy concurrent with those under investigation in this study	Should not be given whilst the patient is on IP treatment
mAbs against CTLA-4, PD-1, or PD-L1	Should not be given whilst the patient is on IP treatment through 90 days after the last dose of IP.
Any concurrent chemotherapy, local therapy (except palliative radiotherapy for non-target lesions, eg, radiotherapy, surgery, radiofrequency ablation), biologic therapy, or hormonal therapy for cancer treatment	Should not be given whilst the patient is on IP treatment (including SoC). (Concurrent use of hormones for non-cancer-related conditions [eg, insulin for diabetes and hormone replacement therapy] is acceptable.)
Immunosuppressive medications, including, but not limited to, systemic corticosteroids at doses exceeding 10 mg/day of prednisone or its equivalent, methotrexate, azathioprine, and tumor necrosis factor α blockers	Should not be given whilst the patient is on IP treatment (including SoC). (Use of immunosuppressive medications for the management of IP-related AEs or in patients with contrast allergies is acceptable. In addition, use of inhaled, topical, and intranasal corticosteroids is permitted.

Prohibited medication/class of drug:	Usage:
Live attenuated vaccines	Should not be given through 30 days after the last dose of IP (including SoC) during the study

Rescue/supportive medication/class of drug:	Usage:
Concomitant medications or treatments (eg, acetaminophen or diphenhydramine) deemed necessary by the Investigator to provide adequate prophylactic or supportive care, except for those medications identified as “prohibited” as listed above	To be administered as prescribed by the Investigator
Best supportive care (including antibiotics, nutritional support, growth factor support, correction of metabolic disorders, optimal symptom control, and pain management [including palliative radiotherapy, etc])	Should be used when necessary for all patients
Best supportive care (including antibiotics, nutritional support, growth factor support, correction of metabolic disorders, optimal symptom control, and pain management [including palliative radiotherapy, etc])	Should be used when necessary for all patients

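### Section 7.2.2 item 3 and Table 4 state opposite corticosteroid limits, with a firm conflict at or below 10 mg/day of prednisone

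*Combined protocol and SAP*

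**What the plan says.** Section 7.2.2 opens its numbered list with "The following medications are considered exclusionary during the study". Item 3 of that list covers immunosuppressive drugs, and its first example is "systemic corticosteroids at doses not exceeding 10 mg/day of prednisone or equivalent". Methotrexate, azathioprine and TNF-alpha blockers follow.

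Table 4, in the same section, has a row for the same class with the same companion drugs. Its corticosteroid entry is "systemic corticosteroids at doses exceeding 10 mg/day of prednisone or its equivalent", and its instruction begins "Should not be given whilst the patient is on IP treatment (including SoC".

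Exclusion criterion 7 in Section 4.2, repeated in the synopsis, bars recent immunosuppressive medication but makes an exception for "systemic corticosteroids at physiological doses, which are not to exceed 10 mg/day of prednisone, or an equivalent corticosteroid".

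Item 3 carries two exceptions that matter here. One is "Use of immunosuppressive medications for the management of investigational product-related AEs or in subjects with contrast allergies is acceptable", which Table 4 also has in near-identical terms. The other is "A temporary period of steroids will be allowed for different indications, at the discretion of the principal investigator", which Table 4 does not have. Both texts permit inhaled and intranasal corticosteroids. Only Table 4 adds topical ones.

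**The concern.** The two entries are plainly meant as one rule: same drug class, same companion drugs, nearly the same exceptions. Yet the dose limit points in opposite directions. Both are current operative text, and the protocol sends staff to each of them. Section 7.2 says the tables that follow describe prohibited medication, which leads to Table 4. Section 7.2.1 permits supportive medication unless Section 7.2.2 lists it as excluded, which leads to the numbered list. Nothing says which prevails.

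At stake is whether a patient on low-dose systemic corticosteroids is following the protocol. One staff member or monitor could record a deviation where another records none. A patient admitted under the exception in criterion 7 would, on item 3 as written, be in breach simply by continuing the same dose.

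**Working it through.** No arithmetic applies. The check sets the passages side by side, taking systemic corticosteroid use in prednisone equivalents to which none of the listed exceptions applies.

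| Daily dose | Section 7.2.2 item 3 | Table 4 row | Exclusion criterion 7 (at entry) |
|---|---|---|---|
| Below 10 mg | Named as excluded | Outside the named range | Physiological dose tolerated |
| Exactly 10 mg | Named as excluded | Outside the named range | Physiological dose tolerated |
| Above 10 mg | Not named, but within reach of the open-ended class wording | Prohibited | Not excepted |

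The first two rows are the firm conflict. In the third, item 3 introduces its drugs as examples of a wider class, so its silence on higher doses is not permission.

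The exceptions compare as follows.

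| Use | Item 3 | Table 4 row |
|---|---|---|
| Managing product-related adverse events | Allowed | Allowed |
| Contrast allergy | Allowed | Allowed |
| Inhaled or intranasal | Allowed | Allowed |
| Topical | Not mentioned | Allowed |
| Temporary course at the principal investigator's discretion | Allowed | Not mentioned |

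Two things follow. First, the shared exceptions remove much steroid use from dispute. Appendix 1 allows retreatment after an endocrinopathy at 10 mg/day or less, and this probably falls under the product-related exception. What remains is mainly low-dose systemic use for other reasons during a treatment period of two doses four weeks apart. Second, above 10 mg/day the texts can still part, but through the exceptions: a short discretionary course has support in item 3 and none in Table 4.

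Last, does anything in the analysis depend on the classification? Section 11.1.1 puts everyone with at least one dose in the safety set. Section 11.1.2 puts all enrolled patients in the feasibility analysis, and requires only specimens and immune measures for the secondary and exploratory analyses. Section 11.6 has no rule for steroid use, and there is no per-protocol set. The definition of extreme toxicity (ETOX) in Sections 3.3 and 11.5 refers to events treatable with steroids, but both texts allow treatment of product-related events. The 15-patient sample and the boundaries in Table 1 are untouched.

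**The case against.** The best defence is that this is a wording slip with little practical reach. There is one center, the principal investigator must be told promptly of any medication taken, and all concomitant medication is recorded. Steroid exposure therefore stays visible whichever label is used. The exceptions cover much of the likely use, and no planned summary changes. All of that stands and sets the size of the point. It does not make the two passages agree.

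A second defence is that Table 4's row is open-ended as well, so it too might reach low doses. On that reading its stated threshold would do no work, and both entries would then conflict with criterion 7. The need to reconcile remains.

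A reader might also infer more than the documents support:

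- **That every dose is classified oppositely**, with item 3 permitting what Table 4 prohibits above 10 mg/day. Item 3's open-ended wording does not support this.
- **That different sites would diverge.** The study has one center.
- **That the paired immune data are compromised.** Immune measures are the secondary endpoint, and the protocol itself classes these drugs as immunosuppressive. But the documents give no effect of doses at or below 10 mg/day on those measures, and no count of patients taking them. One patient is 1/15 to 1/10 of a data set of 10 to 15 (about 7% to 10%). That is only a patient's share of the sample, not the size of any bias.

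**Conclusion.** The contradiction is real and can be verified from the text. It is firm at or below 10 mg/day of prednisone or equivalent, including exactly 10 mg/day. It extends to the entry exception in criterion 7 and to two exceptions that appear in only one of the two texts. Its consequence is inconsistent recording of protocol deviations, and uncertainty for staff about what is allowed. It has no demonstrated effect on any estimate, analysis set or decision rule.

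The number of patients concerned is not given and could be zero. The conclusion assumes that the item 3 and Table 4 entries express one rule, as their near-identical content indicates, and that neither takes precedence, since the protocol names none. It takes no view on which threshold is intended.

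**What to change.** The sponsor should reconcile Section 7.2.2 item 3, the immunosuppressive row of Table 4, and exclusion criterion 7 (with its copy in the synopsis) so that they state one consistent rule. The reconciliation should settle three things:

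- the dose range that is prohibited on study, and how it applies to a patient who entered under the exception in criterion 7;
- whether a temporary discretionary course is allowed;
- whether topical corticosteroids are permitted.

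Which threshold and which exceptions apply is for the sponsor to decide. The cost is a short text correction to the protocol. No sample size, boundary or analysis needs to be redone.
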